**Table 1: Definition of Analysis Days for Diary Data**

Study Period	Diary Day	Study Day a	Time Point
Baseline	Day -7	-7	PM
		-6	AM
	Day -6	-6	PM
		-5	AM
	Day -5	-5	PM
		-4	AM
	Day -4	-4	PM
		-3	AM
	Day -3	-3	PM
		-2	AM
	Day -2	-2	PM
		-1	AM
	Day -1	-1	PM
		1 (pre-dose)	AM
Treatment	Day 1	1	PM
		2	AM
	Day 2	2	PM
		3	AM
	...	..	PM
		..	AM
	Day 251	251	PM
		252	AM

a: Study Day 1 denotes the first dose of study drug; Study Day -1 is the day prior to the first dose of study drug.

## 5. STUDY POPULATION

### 5.1. General

The enrolled analysis set (Section 3.1) will be used for all study population summaries, unless otherwise specified. Summaries will be presented by double-blind treatment group in the previous studies 30025 or 30027 (placebo and reslizumab) and for all patients (ie, total), unless otherwise noted.

For continuous variables, descriptive statistics (number of patients [n], mean, standard deviation [SD], standard error [SE], median, minimum, and maximum) will be provided. For categorical variables, patient counts and percentages will be provided. Categories for missing data will be presented if necessary.

### 5.2. Patient Disposition

Data from patients enrolled, patients enrolled but not treated, patients in the safety analysis set, patients who completed the treatment, patients who completed the study, patients who discontinued from treatment, and patients who withdrew from the study will be summarized using descriptive statistics. Data from patients who discontinue from the treatment and patients who withdrew from the study will also be summarized by reason for withdrawal. The previous study from which patients enrolled (30025 or 30027) will also be summarized, along with whether the patient was a seamless rollover or non-seamless rollover. This summary will include all patients enrolled into this study. The denominator for calculating the percentages will be the number of enrolled patients as appropriate.

### 5.3. Demographics and Baseline Characteristics

Baseline demographics and baseline characteristics, including spirometry and OCS dose, will be summarized using descriptive statistics by previous double-blind treatment group and for all patients.

Age will be calculated based on the date of birth relative to the screening visit (date of informed consent in this study). If regional data regulations prohibit collection of a full date of birth, then the patient's age should be recorded on the CRF, if possible. If only a year of birth has been collected (and age has not otherwise been reported) then the missing date of birth will be imputed as 30 June (30 June YYYY) in order to derive the patient's age at baseline.

### 5.4. Medical History

All medical history abnormalities will be coded using the Medical Dictionary for Regulatory Activities (MedDRA); the final version number will be indicated in the summary tables. The incidence of medical history abnormalities will be summarized by system organ class (SOC) and preferred term (PT). Patients are only counted once in each SOC and once in each PT. Summaries will be presented by previous double-blind treatment group and for all patients.

## **5.5. Prior Therapy and Medication**

Any therapy, medication (including corticosteroids), or procedure a patient has had at screening up to the end of the study period, including follow-up, will be recorded on the appropriate CRF. Generic or trade name, indication, and dosage will be recorded. The sponsor will encode all therapy and medication according to the World Health Organization (WHO) drug dictionary; the final version number will be indicated in the summary tables.

The incidence of prior therapies and medications will be summarized by therapeutic class using descriptive statistics by previous double-blind treatment group and for all patients. Patients are counted only once in each therapeutic class, and only once in each preferred term. Prior therapies and medications will include all medications taken and therapies administered before the first day of reslizumab administration in this study.

## **5.6. Electrocardiography**

Electrocardiogram (ECG) findings (normal, abnormal, and missing) at baseline will be summarized using descriptive statistics by previous double-blind treatment group and for all patients.

## **5.7. Physical Examinations**

Patients with at least 1 abnormal finding (overall) and abnormal findings for each category will be summarized at baseline by previous double-blind treatment group and for all patients.

## **5.8. Childbearing Potential and Methods of Contraception**

For female patients, information related to childbearing potential, contraception, and menopause will be collected at screening. Information will be provided in the patient data listings.

## **5.9. Study Protocol Violation**

Patients with at least 1 protocol violation for each category will be summarized by previous double-blind treatment group and for all patients.

## 6. EFFICACY ANALYSIS

### 6.1. General

The safety analysis set (Section 3.2) will be used for all efficacy analyses unless otherwise noted. Summaries will be presented by double-blind treatment group in the previous studies 30025 and 30027 (placebo and reslizumab) and for all patients (ie, total), unless otherwise noted.

For continuous variables, descriptive statistics (n, mean, SD, SE, median, minimum, and maximum) will be provided. For categorical variables, patient counts and percentages will be provided. Categories for missing data will be presented if necessary.

### 6.2. Primary Efficacy Endpoint and Analysis

There are no pre-specified primary efficacy variables and analyses in this study.

### 6.3. Secondary Efficacy Endpoints and Analysis

#### 6.3.1. Clinical Asthma Exacerbations and Related Healthcare Utilization

##### 6.3.1.1. Definition

A CAE is defined as a clinically judged deterioration in asthma control, as determined by the investigator and evidenced by new or worsening asthma signs or symptoms based on the patient history, handheld eDiary/spirometry data, physical examination, and/or ambulatory or clinic visit assessment of lung function, and that results in a medical intervention, including at least one of the following:

- use of systemic corticosteroids (oral or injection) or at least a doubling from a stable maintenance oral corticosteroid dose for at least 3 days
- asthma-specific hospital admission
- asthma-specific emergency department visit

Additional medication and/or medical intervention that would satisfy the CAE definition occurring within 7 days of the last day of a prior CAE event will be considered as part of the same event for analysis purposes.

All asthma exacerbations (mild/moderate/severe) should be recorded on the asthma exacerbation CRF. The information on the CRF will be used to determine if an asthma exacerbation meets CAE criteria.

The CAE start and stop dates will be collected in order to determine the exacerbation duration. The start date of a CAE will be the start date of the initial medical intervention (eg, use of systemic corticosteroids [oral or injection] or at least a doubling from a stable maintenance oral corticosteroid dose for at least 3 days, asthma-specific hospital admission, or asthma-specific emergency department visit, whichever comes first). The stop date is the last day of systemic corticosteroids or the last day of an asthma-specific hospitalization or emergency department visit, whichever is later. For patients who are on a stable maintenance oral corticosteroid dose

and receive at least a doubling of that dose for 3 days, the stop date is when they return to their baseline dose. For patients receiving a new use of oral corticosteroid or at least a doubling from their stable maintenance oral corticosteroid dose for at least 3 days that did not return to baseline, the CAE stop date will be the day when they have been on a stable dose for at least 10 days.

### **6.3.1.2. Analysis**

Summary statistics of frequency of CAEs and related HCU endpoints (asthma-specific hospital admissions, asthma-specific emergency department visits, school/work days missed due to asthma, and length of hospital stay and number of ICU days) will be provided by previous double-blind treatment group and for all patients. The summary will be presented for clinical asthma exacerbations recorded during the treatment period. For patients who complete treatment, the treatment period will be defined from the first dose of study drug to the end of treatment (week 36) visit. For patients who prematurely discontinue treatment, the treatment period will be defined from the first dose of study drug to the last dose of study drug + 4 weeks. All events will be included in the patient listings. The frequency of CAEs and related HCU endpoints will additionally be examined for the subgroups defined in Section 3.3.

### **6.3.2. Spirometry**

#### **6.3.2.1. Definition**

Pre-bronchodilator (on designated clinic visit days per Table 1 of the protocol; Screening/Baseline and week 8, 24, and 36 or early withdrawal visit) and daily morning ambulatory FEV1 will be measured using the handheld device that has combined spirometry and eDiary capabilities. The FEV1 is the volume of air that can be forcibly exhaled from the lungs in the first second, measured in liters. The National Health and Nutrition Survey (NHANES) III reference equations will be used.

#### **6.3.2.2. Analysis**

Summary statistics of actual values and changes from baseline to each scheduled visit in pre-bronchodilator FEV1 measured using spirometry will be provided by previous double-blind treatment group and for all patients. A line graph presenting the mean change from baseline over time (at each visit) will be provided for prebronchodilator FEV1 by previous double-blind treatment group.

A weekly average of daily morning ambulatory FEV1 (measured by the handheld spirometry device) will be derived using 7-day window intervals based on these analysis days (see Table 1 for the definition of analysis days for diary data). The average will be calculated as the sum of all values divided by the number of non-missing assessments. There will be no imputation of missing data. At least 4 of the 7 measurements need to be recorded for a week to be included in the analysis; otherwise the week will be treated as missing.

Summary statistics of actual values and changes from baseline in weekly average of daily morning ambulatory FEV1 (measured by the handheld spirometry device) at each week through week 36 will be provided by previous double-blind treatment group and for all patients.

FEV1 will additionally be examined for the subgroups defined in Section 3.3.

### 6.3.3. Daily oral corticosteroids dose

#### 6.3.3.1. Definition

OCS dose information is collected in Concomitant Medication CRF page. Doses at Week 20 and 36 will be derived based on the study drug administration visit schedule by comparing OCS medication dates with the start date and end date of each visit ([Table 2](#)). Daily OCS dose is defined as total OCS dose in a day (accounting for reported dose and dose frequency) and converting the total daily dose to a prednisone-equivalent dose ([Table 3](#)).

For patients on maintenance OCS treatment at baseline, the week 20 and 36 OCS dose and corresponding values for absolute and percent change from baseline will be calculated as follows:

- **Baseline dose** = the prescribed OCS dose on the day of first dose of study drug in this study ([Table 2](#)).
- **Dose at week 20 (or 36)** = mean of all daily OCS doses during the period from week 16 to week 20 (or from week 32 to week 36) ([Table 2](#)).
- **Absolute change** = maintenance dose – baseline dose
- **Percent change** =  $100 \times (\text{absolute change} / \text{baseline dose})$

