**4.2.4. Oral Corticosteroid Dose**

The baseline value will be defined as the OCS dose reported on the day of first dose of reslizumab in this study.

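### The week 20 and 36 OCS dose is a window mean of all OCS, including exacerbation courses as written, set against a one-day prescribed baseline; a burst understates the maintenance reduction and can reverse its sign

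*SAP*

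**What the plan says.** The derivation is in SAP 6.3.3.1 and applies to patients on maintenance OCS at baseline.

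- **Source:** "OCS dose information is collected in Concomitant Medication CRF page".
- **Daily dose:** "Daily OCS dose is defined as total OCS dose in a day", converted to a prednisone equivalent.
- **Week 20 (or 36) dose:** "mean of all daily OCS doses during the period from week 16 to week 20", or the matching mean for weeks 32 to 36.
- **Baseline:** "the prescribed OCS dose on the day of first dose of study drug in this study". SAP 4.2.4 words it differently: "The baseline value will be defined as the OCS dose reported on the day of first dose of reslizumab in this study".
- **Absolute change:** "maintenance dose – baseline dose". Percent change divides this by the baseline dose.

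Table 2 starts the week 20 window the day after the W16 visit. The row labelled week 32 to 36 starts the day after the W28 visit, so it nominally covers 56 days and not the 28 that its label implies.

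In SAP 6.3.1.1 one of the interventions that qualifies an event as a CAE is "use of systemic corticosteroids (oral or injection) or at least a doubling from a stable maintenance oral corticosteroid dose for at least 3 days". CAE start and stop dates are collected through the asthma exacerbation CRF. SAP 5.5 requires recording of "Any therapy, medication (including corticosteroids), or procedure a patient has had at screening up to the end of the study period", and Protocol 5.6 adds indication, dosage and dates. Neither document says how OCS given for an exacerbation is handled in the OCS-dose derivation.

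**The concern.** The two sides of the change measure different things: total OCS averaged over weeks on one side, one day's prescription on the other. The formula's label and the restriction to maintenance patients point to a maintenance comparison, as does the design text in SAP 2.1 and Protocol 3.1, but the derivation delivers total exposure.

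At stake is the reading of the OCS-sparing result. A patient whose maintenance dose has come down but who had a short course in the window shows a smaller reduction than was achieved, or an increase. A few such patients can move the mean and widen the SD. The protocol synopsis plans no sensitivity analysis. SAP 2.5.1 puts all planned outputs into the interim report supporting the sBLA.

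**Working it through.** The plan gives no figure for this endpoint, so there is none to reproduce. The check applies the SAP definitions to illustrative patients.

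**Inputs from the documents.** The nominal window *w* is 28 days for week 20. For week 36 it is 28 days by the text and 56 by Table 2. The smallest dose increase that the CAE definition names is a doubling for 3 days. Entry allows maintenance OCS up to 40 mg prednisone daily (Protocol 4.2, criterion j).

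**Assumptions.** Baseline *B*, true fractional maintenance reduction *r*, burst length *b* and burst-day total dose *D* are illustrative. The documents give no typical burst dose or length.

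**Formula.** Window mean = [(w − b) × B(1 − r) + b × D] / w. Percent change = 100 × (mean / B − 1).

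| Patient (mg/day) | Burst | w (days) | Window mean (mg) | Reported | True |
|---|---|---|---|---|---|
| 10 to 5 | 5 d at 40 | 28 | (23×5 + 5×40)/28 = 11.25 | +12.5% | -50% |
| 10 to 5 | 5 d at 40 | 56 | (51×5 + 5×40)/56 = 8.125 | -18.8% | -50% |
| 10 to 5 | 3 d at 10 (doubling) | 28 | (25×5 + 3×10)/28 = 5.54 | -44.6% | -50% |
| 10 to 7.5 | 5 d at 40 | 28 | (23×7.5 + 5×40)/28 = 13.30 | +33.0% | -25% |
| 10 to 7.5 | 5 d at 40 | 56 | (51×7.5 + 5×40)/56 = 10.40 | +4.0% | -25% |
| 20 to 15 | 5 d at 40 | 28 | (23×15 + 5×40)/28 = 19.46 | -2.7% | -25% |
| 10, stable | 5 d at 40 | 28 | (23×10 + 5×40)/28 = 15.36 | +53.6% | 0% |

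**When the sign reverses.** The mean exceeds baseline when D/B > (1 − r) + r × w/b. For a 5-day burst:

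- r = 25%: 0.75 + 0.25×28/5 = 2.15 times baseline in 28 days; 0.75 + 0.25×56/5 = 3.55 times in 56 days.
- r = 50%: 0.50 + 0.50×28/5 = 3.30 times in 28 days; 0.50 + 0.50×56/5 = 6.10 times in 56 days.

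If the burst only doubles the current dose, the sign reverses when r < b/(w + b). For 3 days that is 3/31 = 9.7% in 28 days and 3/59 = 5.1% in 56 days.

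**Group mean.** Suppose every patient is stable on 10 mg and a share has the 5-day, 40 mg burst in a 28-day window. The mean percent change then shifts by 53.6 points times that share: 2.7 points at 5%, 5.4 at 10%, 8.0 at 15%. The shares, the burst and the common baseline are all assumed.

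**Baseline side.** The recent-exacerbation exclusion (Protocol 4.2, criterion h) covers only non-seamless patients. A seamless patient taking 40 mg on the day of Visit 1 for a burst, with unchanged 10 mg maintenance, would show 100 × (10/40 − 1) = -75% if the burst dose were taken as baseline.

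**The case against.** **Inclusion of bursts is inferred.** SAP 6.3.3.1 never mentions them. The formula says maintenance dose, exacerbations have their own CRF, and SAP 5.5 sends medication only to the appropriate CRF. This stands as a caution. Even so, inclusion is the plain reading of a mean over all daily doses with no exclusion.

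**Total OCS is a legitimate measure.** The endpoint in SAP 1.1 is the daily OCS dose, and the maintenance label may be a slip. That stands as far as it goes: total exposure is worth reporting. It does not explain why baseline is measured differently or why the formula carries an undefined term.

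**Stronger readings the documents do not support.** A reader might infer that any burst turns a reduction into an increase. It does not: a 3-day doubling on a 10 to 5 mg taper still gives -44.6%, and a 20 mg baseline tapered to 15 mg with 5 days at 40 mg gives -2.7%. A reader might also infer that every CAE contaminates this endpoint. By SAP 6.3.1.1 an admission or emergency visit alone qualifies, as does injected corticosteroid, and none of these need add OCS. Nor is this double counting: an OCS-treated CAE bears on two endpoints but is counted once in each.

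**The effect is limited.** The analysis is descriptive, in a subset, and SAP 6.1 already reports the median, which dampens a few extreme values. This stands.

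**Conclusion.** The point holds in a conditional form. Following SAP 6.3.3.1 as written, OCS given for an exacerbation above the maintenance dose and inside the window always understates the maintenance reduction. Reversal to an apparent increase needs a burst large relative to baseline or a small true reduction, and is less likely in the 56-day window of Table 2. For the 10 to 5 mg taper the reported change runs from -44.6% (3-day doubling, 28 days) through -18.8% (5 days at 40 mg, 56 days) to +12.5% (5 days at 40 mg, 28 days), against a true -50%. These sizes rest on assumed baselines, tapers and burst courses.

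The error is not one-sided, because a burst on the baseline day would exaggerate the reduction. With no hypothesis test planned, what is affected is the interpretation of one secondary result. This is worth correcting as a cheap improvement.

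**What to change.** Amend SAP 6.3.3.1, 4.2.4 and Table 2:

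1. Define maintenance dose as the mean prednisone-equivalent daily OCS excluding days of temporary exacerbation treatment, identified from the asthma exacerbation CRF dates together with the OCS indication and dates.
2. Apply the same rule at baseline and in both windows. State what is used when the day of first dose falls within a burst; for seamless patients this may need the previous study's medication records.
3. Do not simply drop every CAE day. Where the dose does not return to baseline, SAP 6.3.1.1 ends the CAE only after at least 10 days on a stable dose, so dropping those days would hide a lasting increase. Count the new stable dose as maintenance from its first day.
4. Report total OCS including bursts as a second line.
5. Reconcile the week 32 to 36 window with Table 2's W28 start, and the prescribed with the reported baseline. Table 3, cited for prednisone equivalence, lists inhaled-corticosteroid factors and also needs reconciling.

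The cost is SAP wording and a date merge between data already collected. The downside is that patients with no burst-free day in the window need a stated rule, because SAP 4.3 imputes nothing unless specified. Patient management does not change.

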**Table 2: Definition of Observed Days for OCS Dose**

Visit period	Start day	Stop day
Baseline Dose	Day of first dose of study drug	N/A
Week 16 to Week 20	Day of W16 Visit + 1 day	Day of W20 Visit
Week 32 to Week 36	Day of W28 Visit + 1 day	Day of W36 Visit

**Table 3: Conversion of ICS to Fluticasone-Equivalent Doses**

Inhaled corticosteroid (mcg)	Conversion factor
Fluticasone	1
Fluticasone furoate	2
Mometasone	1.14
Budesonide	0.625
Ciclesonide	1.56
Beclomethasone	1.25
Triamcinolone	0.25

### 6.3.3.2. Analysis

Summary statistics of absolute and percent change in the daily OCS dose at weeks 20 and 36 as compared with the dose at baseline (for patients on daily OCS at baseline) will be provided by previous double-blind treatment group and for all patients.

### 6.3.4. Total reliever bronchodilator medication

#### 6.3.4.1. Definition

Total reliever bronchodilator medication use (inhalations/puffs) will be assessed by reviewing the eDiary that will be maintained by the patient daily, once in the morning and once in the evening. Total reliever use will be derived as the sum of the morning and evening counts.

#### 6.3.4.2. Analysis

A weekly average of total reliever use will be derived (see [Table 1](#) for the definition of analysis days for diary data). The average will be calculated as the sum of all values divided by the number of non-missing assessments. There will be no imputation of missing data. At least 4 of the 7 measurements need to be recorded for a week to be included in the analysis; otherwise the week will be treated as missing.

Summary statistics of actual values and change from baseline in total inhalations of reliever bronchodilator medication measured using weekly averages to each week through week 36 will be provided by previous double-blind treatment group and for all patients.

### 6.3.5. Asthma Control Questionnaire

#### 6.3.5.1. Definition

The ACQ-6 is a validated asthma assessment tool that has been widely used. There are 6 self-assessment questions. Each item on the ACQ-6 has a possible score ranging from 0 to 6 (higher scores are an indication of poorer asthma control), and the total score is the mean of all responses. At weeks 0, 8, 24, and 36 (or early withdrawal), the patient answers each of the 6 questions, identifying the response that best describes how the patient has been during the past week.

#### 6.3.5.1.1. Missing data handling and total score calculation

The overall score of the ACQ-6 is derived as the average of the individual item scores; the analysis will be based on the available data.

For incomplete data, the following rules will apply:

1. Total score for the visit will not be calculated if Question 1 is left blank, irrespective of the completion of the remaining questions.
2. A missing score on post screening questionnaire for Questions 2-6 will be imputed based on the total scores from the previous visit, as long as at least 3 out of the 5 questions have responses for the current visit (ie, at least half of the remaining questions are answered).

The formula is: (total sum of non-missing scores for the current visit / total sum of scores for the previous visit for questions answered for the current visit) \* (score for the missing question on the previous visit)

3. Total score at screening will not be calculated if Question 1 or two or more among Questions 2-6 is left blank. A missing score for Questions 2-6 at screening will be replaced by an average of the available scores.

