9.3. Data Handling Conventions

For all variables, only the observed data from the patients will be used in the statistical analyses; that is, there is no plan to estimate missing data.

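### The ACQ-6 missing-item formula has no rule for a zero denominator and no upper bound, so it can return no value or an item score above the scale maximum of 6

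*SAP*

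**What the plan says.** SAP 6.3.5.1 sets the scale: "Each item on the ACQ-6 has a possible score ranging from 0 to 6". SAP 6.3.5.1.1 sets the total: "The overall score of the ACQ-6 is derived as the average of the individual item scores".

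Three rules for incomplete forms follow in SAP 6.3.5.1.1:

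- **Rule 1:** no total if Question 1 is blank.
- **Rule 2 (post-screening):** a blank among Questions 2 to 6 is imputed "as long as at least 3 out of the 5 questions have responses for the current visit". The imputed value is a ratio, "total sum of non-missing scores for the current visit / total sum of scores for the previous visit", times a multiplier. The denominator is limited to the items answered now: "total sum of scores for the previous visit for questions answered for the current visit". The multiplier is the "score for the missing question on the previous visit".
- **Rule 3 (screening only):** a single blank among Questions 2 to 6 is replaced by the average of the available scores. With two or more blank, no total is calculated.

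Rule 2 states no alternative for a denominator of 0 and no limit on the result. SAP 4.3 and Protocol 9.3 and 9.3.1 supply neither.

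**The concern.** A score of 0 is permitted on every item, so the denominator can be 0. The ratio has no ceiling and multiplies a score that can itself be as high as 6, so the product can leave the scale. A programmer applying rule 2 literally will meet forms with no answer, and forms where the answer is a score no patient could have given.

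At stake is the change from baseline in ACQ-6, a secondary efficacy endpoint summarised at each scheduled visit and plotted by previous double-blind group (SAP 6.3.5.2). The zero-denominator case would be settled during programming rather than in advance. The above-6 case can pass unnoticed, because a total built on an impossible item may still lie between 0 and 6.

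**Working it through.** The SAP gives no worked example of the rule, so there is no stated figure to reproduce. The check applies the formula directly.

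**Inputs**
- Item range 0 to 6 (SAP 6.3.5.1).
- Total = mean of the 6 items (SAP 6.3.5.1.1).
- C = sum of the items answered now. P = previous-visit sum of those same items. m = previous-visit score of the missing item (SAP 6.3.5.1.1, rule 2).

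**Formula:** imputed item = (C / P) × m.

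**Step 1. Ordinary input.** Five current answers of 2, the same items previously 3, m = 3: (10 / 15) × 3 = 2.0. The rule behaves sensibly here.

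**Step 2. Zero denominator.**
- All six items previously 0, five current answers of 0: (0 / 0) × 0, undefined.
- Answered items previously 0, m = 2, five current answers of 1: (5 / 0) × 2, undefined.

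P covers only the items answered now. The failure therefore takes in every patient whose previous total was 0, and also a patient whose only non-zero previous item is the one now blank.

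**Step 3. When the result exceeds 6.** (C / P) × m > 6 whenever C / P > 6 / m:

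| m | Ratio C / P above which the item exceeds 6 |
|---|---|
| 1 | 6.0 |
| 2 | 3.0 |
| 3 | 2.0 |
| 4 | 1.5 |
| 5 | 1.2 |
| 6 | 1.0 |

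With m = 6, any worsening in the sum of the answered items takes the imputed item off the scale.

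**Step 4. Two examples.**
- *A.* Previous answered items all 2, m = 5, current answers all 3. Item = (15 / 10) × 5 = 7.5. Total = (15 + 7.5) / 6 = 3.75. The largest attainable total, with the blank item at 6, is (15 + 6) / 6 = 3.50.
- *B.* Previous Questions 1 to 5 = 1, 0, 0, 0, 0 and Question 6 = 1. Current Questions 1 to 5 = 2, 2, 1, 2, 1, Question 6 blank. Item = (8 / 1) × 1 = 8. Total = (8 + 8) / 6 = 2.67. The largest attainable total is (8 + 6) / 6 = 2.33, and the mean of the five answers is 8 / 5 = 1.60.

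Both totals lie inside 0 to 6, so a range check on the total would not catch them. The check has to be on the imputed item.

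**Step 5. Does it matter whether Question 1 is in the sums?** The examples include it. Without it, A is unchanged, (12 / 8) × 5 = 7.5, and B becomes 6 / 0, undefined. The problem remains on either reading.

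**Step 6. Scale of effect.** About 360 patients (SAP 2.4) and three post-baseline ACQ-6 visits (weeks 8, 24 and 36) give at most 360 × 3 = 1,080 forms. If 2% to 5% had a blank item (an assumption, since the documents give no rate), that is about 22 to 54 forms, of which only some would fail. One form like B differs from the mean-of-answers total by 2.67 − 1.60 = 1.07 points. On a visit mean over 360 patients that is 1.07 / 360 ≈ 0.003 points.

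**The case against.** The strongest reply is that this hardly matters. The study is descriptive (Protocol 9.5.2), the primary endpoint is adverse events, only incomplete forms are touched, and example B needs an eightfold rise in the sum of the answered items. All of that stands as a limit on size. It does not supply the missing rule, and example A needs only a rise from 2 to 3 in each answer.

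A reader might also infer more than the documents support:

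- **That the imputation breaches the protocol.** Protocol 9.3 does say "there is no plan to estimate missing data". But Protocol 9.3.1 and SAP 4.3 both allow imputation where it is specified, and rule 2 is such a specification. There is no departure, and no entry in SAP Table 7 is needed.
- **That a zero denominator loses the visit.** The SAP does not say so. Its general statement that the analysis uses available data would equally permit averaging the answered items. The fault is silence.
- **That the rule fails where most extension patients will score.** No ACQ-6 distribution is given, and the population is described as inadequately controlled on standard care.
- **That the ratio formula should be replaced by the mean of answered items because rule 3 already does this.** Rule 3 refuses a score when two or more of Questions 2 to 6 are blank, whereas rule 2 allows two blanks. An item previously at 0 is always imputed as 0 when the formula is defined, but that is inherent in scaling a previous score. The mean of answers has its own error when one item usually differs from the rest. The choice between the two is a trade-off.

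**Conclusion.** The point holds as a gap in a scoring rule. As written, rule 2 can return no value when the answered items were all 0 at the previous visit, and can return an item above 6 whenever the ratio exceeds 6 divided by the missing item's previous score. Both follow from the SAP's own text and need no assumption about the data.

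The size is small. How often either failure would occur depends on the rate of incomplete forms and the score distribution. The documents give neither, so any percentage would rest on invented inputs. The 2% to 5% used above only illustrates scale. The primary safety endpoint is unaffected.

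**What to change.** Keep the ratio formula in SAP 6.3.5.1.1, rule 2, and add one sentence with two parts:

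1. Limit the imputed item to the range 0 to 6.
2. When the previous-visit sum of the answered items is 0, replace the missing item with the mean of the items answered at the current visit.

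With the limit, example A scores 3.50 and example B 2.33. With the fallback, previous answered items of 0 and five current answers of 1 give an imputed item of 1 and a total of (5 + 1) / 6 = 1.00.

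No new data are needed, and only forms with an undefined or above-6 result change. There are two limits. The cap makes the score possible, not necessarily accurate: example B still imputes 6 beside answers of 1 and 2. And for seamless rollovers the ACQ-6 baseline comes from the parent study's end-of-treatment visit (SAP 4.2.3). If the parent studies used the unbounded formula, the few affected forms would be scored slightly differently from theirs. The documents do not show which rule the parent studies used.
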